- (d) Vital sign measurements include blood pressure (diastolic and systolic), heart rate, and temperature.
- (e) Single, 12-lead ECGs will be collected according to the schedule presented in the [Phase 1b Pharmacokinetic and ECG Sample Breakdown](#) and the [Phase 2 Pharmacokinetic and ECG Sample Breakdown](#) table. When the timing of an ECG coincides with blood samples for PK, the ECG should be completed first.
- (f) Contrast-enhanced imaging CT or MRI of the chest, abdomen, and pelvis must be obtained at baseline within 4 weeks before the first dose of MLN0128. Unless contraindicated, such contrast-enhanced imaging CT or MRI scans will be obtained every 2 cycles from Cycle 2 through Cycle 6 (ie, Cycle 2 Day 28, Cycle 4 Day 28, and Cycle 6 Day 28) and then every 3 cycles thereafter (ie, Cycle 9 Day 28, Cycle 12 Day 28, Cycle 15 Day 28, etc). A confirmatory scan should be performed at approximately 4 weeks from the previous scan for all patients with a complete or partial response. For those patients who have documented radiographic disease progression, CT or MRI scans are not required at the EOT visit. The same imaging modality (CT or MRI) should be used throughout the study.
- (g) After EOT, patients will be followed for PFS and OS; see Section 7.10 for more details. For those patients who discontinue MLN0128 for any reason other than radiographic disease progression, contrast-enhanced imaging CT or MRI scans should be completed to further assess disease progression (per RECIST, version 1.1).
- (h) Including serious pretreatment events; see Section 9.1.1.
- (i) Exemestane or fulvestrant should be administered according to the USPI or SmPC and according to the dose administered during previous treatment.
- (j) May be assessed up to 24 hours before the study visit.
- (k) For screening, creatinine clearance must be  $\geq 50$  mL/min based either on Cockcroft-Gault estimate or based on a 12- or 24-hour urine collection.
- (l) Coagulation assessment is required for all patients at times specified in the [Schedule of Events](#). When a tumor biopsy is required, coagulation assessment is required within 24 hours before obtaining the tumor biopsy. See Section 7.4.19 for additional information regarding tumor biopsy.
- (m) Fasting serum glucose will be measured in the clinic. Patients are required to fast overnight (nothing except water and/or medications after midnight or for a

	Screening (a)	TREATMENT CYCLES										EOT/ ET (b)	PFSFU /OSFU

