#### **7.10 Posttreatment Follow-up Assessments (PFS and OS)**

After EOT, patients will be followed for PFS and OS. Survivor information may be collected by methods that include, but are not limited to, telephone, email, mail, or retrieved from online or other databases (eg, Social Security indexes). In addition, the start of another anticancer therapy will be collected. For those patients who discontinue MLN0128 for any

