7.8.2 Secondary Efficacy Endpoint(s)

Phase 2

Clinical benefit rate at 24 weeks (CBR-24)

The CBR-24 is defined as the proportion of patients who achieve CR or partial response of any duration, or have SD at 24 weeks.

The number and percentage of patients achieving CBR-24 will be summarized by cohort and combination partner (Exemestane or Fulvestrant) within each cohort. The estimate of the CBR-24 will be presented with a 2-sided 95% exact binomial confidence interval. The CBR-24 will be determined based on both unconfirmed and confirmed best overall response (see Section 7.8.3 Additional Efficacy Endpoints for definitions) for the response-evaluable population.

SD for at least 24 weeks is a subset of SD, only calculated for those patients with a best response of SD. It is defined as SD at the end of Cycle 2, Cycle 4, and Cycle 6 (see exception below).

CBR at 24 weeks (unconfirmed) is defined as the number of patients who achieve CR or PR at any time or have SD for at least 24 weeks.

CBR at 24 weeks (confirmed) is defined as the number of patients who achieve confirmed CR or confirmed PR at any time or have SD for at least 24 weeks or meet the following criteria:

Overall response at end of Cycle 2	Overall response at end of Cycle 4	Overall Response at the end of Cycle 6
CR/PR (unconfirmed)	SD	SD
SD	CR/PR (unconfirmed)	SD
SD	SD	CR/PR (unconfirmed)

Overall response rate (ORR)

The ORR is defined as the proportion of patients with a best response of CR or partial response. The number and percentage of patients achieving an ORR will be summarized by cohort and combination partner (Exemestane or Fulvestrant) within each cohort. The estimate of the ORR will be presented with a 2-sided 95% exact binomial confidence interval. The ORR will be determined based on both unconfirmed and confirmed best overall response (see Section 7.8.3 Additional Efficacy Endpoints for definitions) for the response-evaluable population.

Progression-free survival (PFS)

Progression-free survival is defined as the time from the date of first MLN0128 administration to the date of first documentation of disease progression or death due to any cause, whichever occurs first. Progression is based on the investigator response assessment per RECIST 1.1 criteria.

PFS in months is defined as:

(earliest date of progression or death – date of first dose of MLN0128 + 1)/30.4375

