In the event of progression, the date of progression is defined as the earliest date among target lesions, non-target and new lesions dates at that particular visit. For a patient whose disease has not progressed and is last known to be alive, PFS will be censored at the last response assessment that is SD or better.

The approach for handling of missing response assessments and censoring is presented in [Table 7.a](#).

Table 7.a Handling of Missing Response Assessment and Censoring

Situation	Date of Progression or Censoring	Outcome
No baseline tumor assessment	Randomization	Censored
No post baseline tumor assessment and no death	Randomization	Censored
Disease progression documented between scheduled visits	Date of first documented disease progression	Progressed
Disease progression documented subsequent to missing 2 or more adequate tumor assessments	Date of first documented disease progression	Progressed
No documented disease progression or no death	Date of last adequate assessment	Censored
Alternate subsequent therapy started prior to disease progression	Date of last adequate assessment prior to the start of subsequent therapy	Censored
Death without progression and without subsequent anti-cancer therapy	Date of death	Progressed
Adequate Assessment: investigator response assessment other than Unable to Assess, unknown or missing (i.e. CR, PR, SD or PD).		

PFS Analysis

The Kaplan-Meier method will be used to analyze the distribution of PFS for the Safety Population. Kaplan-Meier survival curves, the 25th, 50th (median), and 75th percentiles, along with associated 2-sided 95% confidence intervals (CIs) based on Brookmeyer and Crowley, and Kaplan-Meier estimates with 95% CIs at 6, 12 and 18 and 24 months will be presented.

The source of PFS (death or progressive disease) and the status of subjects who are censored in the PFS Kaplan-Meier analysis [no post baseline tumor assessment and no death, on-study (on treatment, in follow-up), Lost to follow-up, and received subsequent anti-cancer therapy] will be tabulated.

PFS will be summarized by cohort and combination partner (Exemestane or Fulvestrant) within each cohort.

Overall survival (OS)

Overall survival in months is defined as: (date of death – date of first dose of MLN0128 + 1) / 30.4375. Patients without documentation of death at the time of analysis will be censored at the

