7.8.3 Additional Efficacy Endpoint(s)

Best Overall Response

Best Overall Response (unconfirmed): The best response after the first dose of study drug until subsequent therapy ordered from best to worst: Complete Response, Partial Response, Stable Disease, Progressive Disease. The best response can also be Unable to Assess, Unknown, or No assessment performed if this is the only investigator assessment of objective response available for the patient.

Best Overall Response (confirmed): The best response after the first dose of study drug until subsequent therapy ordered from best to worst: Complete Response, Partial Response, Stable Disease, Progressive Disease. The best response can also be Unable to Assess, Unknown, or No assessment performed if this is the only investigator assessment of objective response available for the patient.

Complete or partial responses may be claimed as best response only if the criteria for each are met at a subsequent time point. For the best overall response (confirmed), the confirmation derivation rules will be as described in the following table.

Confirmation Derivation Rules		
Overall response 1 st time point	Overall response subsequent time point	BEST overall response
CR	PR	PR
CR	SD	SD
CR	PD	SD
CR	NE	SD
PR	CR	PR
PR	PR	PR
PR	SD	SD
PR	PD	SD
PR	NE	SD
NE	NE	NE

Note: No adjustment for minimum criteria for SD is needed as the first protocol scan is at the end of cycle 2, approximately 8 weeks from first dose.

The number and percentage of patients in each response category (CR, PR, SD, SD-16, SD-24, Progressive Disease, Unable to Assess, Unknown, or no post baseline response assessment) will be summarized by cohort and combination partner (Exemestane or Fulvestrant) within each cohort.

Duration of Response (DOR)

The duration of objective response will be calculated for those patients with a best response of CR or PR, and is defined as the number of days from the start date of CR, or PR (whichever response is achieved first) until progressive disease or until the last response assessment if there is no progressive disease. For phase 2 the Kaplan-Meier method will be used to analyze the DOR. Kaplan-Meier survival curves, the 25th, 50th (median), and 75th percentiles, along with associated 2-sided 95% confidence intervals (CIs) based on Brookmeyer and Crowley will be presented.

Duration of Stable Disease

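### Duration of response ends only at progression, so a responder who dies without documented progression is in effect censored at her last scan, although PFS counts such a death as an event

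*SAP*

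**What the plan says.** **DOR (SAP 7.8.3).** The population is responders: "The duration of objective response will be calculated for those patients with a best response of CR or PR". The clock starts at the first CR or PR and runs "until progressive disease or until the last response assessment if there is no progressive disease". The method is given next: "For phase 2 the Kaplan-Meier method will be used to analyze the DOR", with quartiles and Brookmeyer-Crowley confidence intervals. In phase 1b, DOR is only listed (SAP 7.8).

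**PFS (SAP 7.8.2).** The event is the "date of first documentation of disease progression or death due to any cause, whichever occurs first". Table 7.a has a row for "Death without progression and without subsequent anti-cancer therapy", which takes the date of death and counts as an event. A patient who starts other therapy before progression is censored at the last adequate assessment before that therapy. The SAP also tabulates the source of each PFS event, with death and progressive disease as separate categories.

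**Elsewhere.** The protocol does not define DOR. Protocol 7.10 says "After EOT, patients will be followed for PFS and OS", so the dates needed to handle death are already sought. Protocol 8.1.6 makes the efficacy analysis descriptive.

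**The concern.** A response ends when the patient progresses or dies. The DOR sentence offers two endings, progressive disease or the last assessment without it, and every responder falls under one of them. A woman who dies in response falls under the second. Her time stops at her last scan with no event, and the Kaplan-Meier curve then treats her like a living responder who has not been followed further.

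Two things are at stake. The reported median and quartiles would describe time to progression with deaths set aside, while a reader would normally take them as how long patients stayed alive and in response. DOR and PFS would also follow different conventions within one report: some patients would have a PFS event at death and an apparently continuing response.

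**Working it through.** The documents state no expected DOR, number of responders or number of deaths, so there is no figure to reproduce. The check has two parts.

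**1. Reading the rules side by side: a responder who dies with no documented progression and no other therapy**

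| Endpoint | Rule | Result |
|---|---|---|
| PFS | SAP 7.8.2 definition and the Table 7.a death row | Event at date of death |
| DOR | SAP 7.8.3, no progressive disease | Time to last assessment, no event |

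Could another passage supply the missing rule? Table 7.a sits under PFS, and the DOR text does not refer to it. Progressive disease cannot be read as including death, because the PFS text lists the two as separate event sources. The PFS censoring sentence is limited to patients last known to be alive; the DOR sentence has no such limit. The SAP does not use the word censored for DOR, but that is the only reading that fits a Kaplan-Meier analysis with progression as its sole event.

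**2. Size, under assumptions**

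Let h1 be the hazard of documented progression and h2 the hazard of death without it, both constant and independent. Let f = h2/(h1 + h2).

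- Median time to progression or death: ln 2/(h1 + h2)
- Median that Kaplan-Meier estimates with deaths censored: ln 2/h1
- Ratio: (h1 + h2)/h1 = 1/(1 - f)

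Take a median time to progression or death of 6 months (an assumption, for illustration). By 12 months two half-lives have passed, so 0.5 × 0.5 = 25% remain when death is an event. With deaths censored at death, the 12-month value is 0.25^(1-f).

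In practice the deaths would be censored at the preceding scan. Imaging is "every 2 cycles from Cycle 2 through Cycle 6" and then every 3 cycles, with 28-day cycles. If response starts at the end of Cycle 2, the scan intervals after it are 56, 56, 84, 84 and 84 days, reaching day 364. If S is the probability of passing an interval free of both progression and death, the Kaplan-Meier factor for that interval is S/(S + (1-f)(1-S)). Six months is 6 × 30.4375 = 182.6 days, so S = 0.5^(56/182.6) = 0.809 or 0.5^(84/182.6) = 0.727.

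At f = 10% the factors are 0.809/(0.809 + 0.9 × 0.191) = 0.824 (twice) and 0.727/(0.727 + 0.9 × 0.273) = 0.747 (three times). Their product is 0.28.

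| Assumed f | Median ratio 1/(1-f) | Median, months | 12-month DOR, censored at death | 12-month DOR, censored at last scan |
|---|---|---|---|---|
| 0% | 1.00 | 6.0 | 25% | 25% |
| 5% | 1.05 | 6.3 | 27% | 27% |
| 10% | 1.11 | 6.7 | 29% | 28% |
| 20% | 1.25 | 7.5 | 33% | 32% |
| 30% | 1.43 | 8.6 | 38% | 37% |

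A simulation of 200,000 responders on the same scan schedule gave 27%, 28%, 32% and 37% for f = 5%, 10%, 20% and 30%, in agreement with the last column.

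**Direction.** The lengthening is a tendency, not a certainty in each data set. Moving a patient's exit back to her last scan shrinks the risk set early, so in a small sample a single later progression can produce a larger step down.

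**The case against.** Several objections are fair, and each limits the point.

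- **The ratio is not a measure of informative censoring.** A reader might infer that 1/(1-f) shows Kaplan-Meier to be biased by informative censoring. It does not. Under the independent hazards that produce the formula, Kaplan-Meier with deaths censored correctly estimates time to progression. The ratio is the gap between two endpoints, and calling the result too long requires taking progression or death as the target. The SAP takes that target for PFS but does not state one for DOR.
- **The effect is conditional.** If no responder dies before documented progression, nothing changes. The documents give no value for f.
- **Numbers will be small.** At the target rates, clinical benefit is about 0.20 × 56 = 11 resistant and 0.30 × 48 = 14 sensitive patients. Those counts include stable disease, so responders are likely to be fewer. Large-sample percentages suggest more precision than the data will have. Equally, one or two deaths could move a median noticeably.
- **Not every death creates a conflict with PFS.** A patient who started other therapy before progression is censored in PFS as well. The mismatch is confined to deaths without subsequent therapy.
- **Deaths are not hidden.** PFS and OS count them, and the source of PFS events is tabulated.

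None of these defends leaving death out of the DOR rule. They limit how strongly the consequence can be put.

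**Conclusion.** The point holds in a limited form. As written, SAP 7.8.3 in effect censors at her last scan a responder who dies without documented progression, while PFS counts the same patient as an event if she had no other therapy. If such deaths occur, the reported DOR will tend to exceed the time to progression or death. Under constant independent hazards the medians differ by about 5% at f = 5%, 11% at 10%, 25% at 20% and 43% at 30%. All of these f values are assumptions.

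A reader might go further and infer that the reported DOR is bound to be overstated, or that the trial's efficacy conclusion is at risk. The documents support neither. The first depends on an unknown f. The second fails because DOR is not among the primary or secondary endpoints, is descriptive, and does not enter CBR-16, the sample size or the futility boundaries. The change is worth making because the present rule answers a less useful question and the remedy is almost free.

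**What to change.** Replace the DOR sentence in SAP 7.8.3 with a definition along these lines: time from the first CR or PR to the earlier of documented progression or death from any cause; patients alive without documented progression are censored at the last adequate assessment.

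State that the Table 7.a rules for subsequent therapy and for missed assessments apply to DOR. The subsequent-therapy rule is a separate change, because DOR has none now, and should be labelled as such. The two rows of Table 7.a that refer to randomization do not arise, since a responder has both a baseline and a post-baseline assessment. The row that joins no progression and no death with the word or should be read for DOR as neither having occurred.

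The listed duration of stable disease has the same wording and could be aligned at the same time.

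The cost is one SAP sentence and a small code change, with no new data, because deaths are already followed for PFS and OS. The reported DOR may be shorter.

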7.8.4 Exploratory Efficacy Endpoints

CCI

CCI

7.9 Pharmacokinetic/Pharmacodynamic Analysis

7.9.1 Pharmacokinetic Analysis

The PK of MLN0128 on Cycle 1 Day 15 and Cycle 2 Day 1 obtained during the phase 1b (Parts 1 and 2) will be assessed based on evaluable patients. The MLN0128 plasma concentrations collected during the phase 2 will be included in data listings in the clinical study report.

The exemestane plasma concentrations obtained in the phase 1b (Parts 1 and 2) will be presented in data listings in the clinical study report; however, no exemestane PK parameters will be estimated and/or reported, due to the limited amount of PK evaluable data.

For the purposes of assessing a potential DDI between MLN0128 and exemestane on MLN0128, plasma concentration-time data and relevant PK parameters (such as C_{max} , AUC_{24h} , and $t_{1/2}$) of MLN0128 will be compared against historical single-agent PK data. The results of this PK evaluation will not be part of the clinical study report.

In addition, PK data generated during the phase 1b and phase 2 in this study may be combined with data from other studies in which the PK of MLN0128 is characterized for population PK analysis. The results of population PK analysis will be presented in a separate report. This will include the sparse PK data collected during the phase 2 portion of the study.

PK data from the phase 1b portion of the study will be summarized as described below.

Pharmacokinetic Concentrations

Descriptive statistics (number of patients, arithmetic mean, arithmetic standard deviation, arithmetic coefficient of variation, geometric mean, geometric coefficient of variation, median,

minimum, and maximum) will be used to summarize the MLN0128 plasma concentrations. For the estimation of mean concentration in plots and tabular summaries, BLQ values will always be replaced by zero.

Linear and semi-logarithmic plots of the mean (+SD) MLN0128 plasma concentrations versus scheduled sampling times will be provided for each intense sampling study visit (Cycle 1 Day 15 and Cycle 2 Day 1) segregated by treatment group, as follows:

1. MLN0128 5 mg QD [unmilled API, light meal] + Exemestane.
2. MLN0128 5 mg QD [unmilled API, light meal] + Fulvestrant.
3. MLN0128 3 mg QD [milled API, empty stomach] + Exemestane.
4. MLN0128 3 mg QD [milled API, empty stomach] + Fulvestrant.
5. MLN0128 4 mg QD [milled API, empty stomach] + Exemestane.

Linear and semi-logarithmic plots of individual MLN0128 plasma concentrations versus actual sampling time will be provided for each treatment group and segregated by study visit (Cycle 1 Day 15 and Cycle 2 Day 1) eg, for MLN0128 the Cycle 1 Day15 and Cycle 2 Day 1 will be overlaid on the same plot.

In all Cycle 1 Day 15 MLN0128 plasma concentration versus time plots, pre-dose concentrations will be duplicated and the replicate value will then be imputed as the 24-hour post-dose concentration, thereby extending the PK profile from 8 hours to 24 hours.

All individual patient plasma MLN0128 and exemestane concentration data will be presented in a data listing. MLN0128 imputed 24-hour concentration values will be flagged in listings and will be accompanied by an appropriate footnote.

Pharmacokinetic Parameters

PK parameters will be estimated using non-compartmental methods with WinNonlin[®] Professional Version 7.0 or higher (Certara USA, Inc., Princeton, NJ). The plasma PK parameters will be estimated from the concentration-time profiles for all PK population patients. In estimating the PK parameters, BQL values at the beginning of the profile will be set to zero. BQL values that occur after the first quantifiable point will be considered missing. Values that are embedded between BQLs, or quantifiable values occurring after two or more BQLs, will be set to missing at the discretion of the pharmacokineticist. Actual sampling times, rather than scheduled sampling times, will be used in all computations involving sampling times. If an actual time is missing the nominal time may be used.

In addition, for the estimation of the Cycle 1 Day 15 MLN0128 plasma PK parameters, pre-dose concentrations will be duplicated and the replicate value will then be imputed as the 24-hour post-dose concentration, thereby extending the PK profile from 0 to 8 hours to 0 to 24 hours. Hence, all Cycle 1 Day 15 PK parameters will be derived over a period of 24 hours.

All individual patient PK parameter data will be in a data listing. Descriptive statistics (number of patients, arithmetic mean, arithmetic standard deviation, arithmetic coefficient of variation,

median, minimum value, and maximum value) will be used to summarize the calculated PK parameters. Additionally, geometric mean and geometric coefficient of variation will be calculated for concentration parameters (such as C_{\max} and C_{trough}) and AUC parameters (such as AUC_t and AUC_{24h}), clearance parameters (CL/F), and volume parameters (V_z/F). For T_{\max} , only median, minimum value, and maximum value will be presented.

Descriptive statistics reported in the main body of the CSR will include sample size, geometric mean and geometric coefficient of variation for concentration, AUC, clearance and volume parameters; arithmetic mean, coefficient of variation, and sample size will be reported for λ_z and $t_{1/2}$; and median and range for T_{\max} .

Data permitting, the following steady-state PK parameters will be calculated for MLN0128 following Cycle 1 Day 15 by noncompartmental analysis:

- Observed maximum plasma concentration (C_{\max}).
- Time to observed maximum plasma concentration (T_{\max}).
- Area under the plasma concentration-time curve from time 0 to time of last measurable concentration (AUC_t).
- Area under the plasma concentration versus time curve from zero to 24 hours (AUC_{24h}).
- Area under the plasma concentration-time curve from time 0 to 4 hr (AUC_{4h}).
- Area under the plasma concentration-time curve from time 0 to 8 hr (AUC_{8h}).
- End of dosing interval (trough) concentration (C_{trough}).
- Terminal disposition half-life ($t_{1/2}$).
- Apparent oral clearance (CL/F).
- Apparent terminal phase volume of distribution (V_z/F).

The following Cycle 1 Day 15 PK parameters will also be reported in a separate listing of supplementary PK parameters:

- Terminal phase number of data points (Number).
- Upper time for calculation of terminal elimination rate constant (λ_z upper).
- Lower time for calculation of terminal elimination rate constant (λ_z lower).
- Terminal disposition phase rate constant (λ_z).
- Terminal phase regression adjusted R^2 (R^2_{adj}).

Data permitting, the following steady-state PK parameters will be calculated for MLN0128 following Cycle 2 Day 1 by noncompartmental analysis:

- C_{\max} .
- T_{\max} .

- AUC_t.
- AUC_{4h}.

Descriptive statistics will be presented for the MLN0128 plasma PK parameters on Cycle 1, Day 15 and Cycle 2, Day 1 for the following groups:

1. MLN0128 5 mg QD [unmilled API, light meal] + Exemestane.
2. MLN0128 5 mg QD [unmilled API, light meal] + Fulvestrant.
3. MLN0128 3 mg QD [milled API, empty stomach] + Exemestane.
4. MLN0128 3 mg QD [milled API, empty stomach] + Fulvestrant.
5. MLN0128 4 mg QD [milled API, empty stomach] + Exemestane.

Dot plots of selected PK parameters vs treatment group will be generated for Cycle 1 Day 15 (C_{max}, AUC_{4h}, AUC_{8h} and AUC_{24h}) and Cycle 2 Day 1 (C_{max}, AUC_{4h}).

